Prevalence of lung cancer in China is about 36.09/10 million, with mortality of 28.41/10 million. The prevalence of sarcopenia in Asia is 25.2%. Combined with reported correlation coefficient OR3.2 of tumor and sarcopenia, GPOWER is used to calculate the incomplete information and missing value below 10%. α Less than or equal to 0.05 and statistical inspection force $1 - \beta$ When it is 0.8, it is estimated that the final required numbers for this study includes about 66 patients with lung cancer complicated with sarcopenia. According to the 1:1 ratio of sarcopenia and non sarcopenia, the overall sample size is about 132, so as to ensure that the efficiency of the control test is 80%.

6、 Research process

1. Demographic data

The gender, age, height, weight, body mass index and skeletal muscle mass index were recorded.

2. Clinical data

According to the Electronic Medical Record, system image record data, face-to-face or

telephone follow-up records, clinical data were collected: oral drugs, smoking status (no smoking history, past smoking history, now smoking), tumor stage at the time of diagnosis, other chronic diseases, tumor pathological type and stage. According to the definition of tumor, lymph node and metastasis TNM stage in the eighth edition of American Lung Cancer joint staging. ECOG (Eastern Cooperative Oncology Group performance status, PS), MNA (mini nutritional assessment) nutrition score, quality of life depression score and treatment strategy.

3. Examination data

Serological samples: blood routine, C-reactive protein, blood cholesterol level, albumin level, tumor markers CEA, cyfra211, NSE, SCC, EGFR gene expression.

Imaging examination: chest CT.

4. Diagnostic criteria of sarcopenia

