The diagnosis process of sarcopenia complies with the provisions of the Asian sarcopenia working group. The specific information collected for diagnosis includes: skeletal muscle mass of limbs: the skeletal muscle mass index (ASMI) is measured by Korea inbody570 (Korea Biospace) human composition analyzer. The decrease of skeletal muscle mass is defined as the decrease of male $< 7.0\text{kg}/\text{m}^2$ and female $< 5.7\text{kg}/\text{m}^2$; The Jamar hand dynamometer (USA) is used to measure the grip strength in the grip strength test. Patients are required to hold the grip strength tester in the dominant hand with standing position for 3 times, the maximum value were recorded. Male $< 28\text{kg}$ and female $< 18\text{kg}$ are defined as reduced grip strength; The time required for patients to walk at normal pace was measured by 6-meter distance pace measurement; If the walking speed is less than $0.8\text{m}/\text{s}$, it is defined as the decline of walking function; The decrease of ASMI accompanied by the decrease of grip strength or gait speed was diagnosed as sarcopenia.

5. Follow up endpoint

The primary endpoint was progression free survival (PFS) within 2 years, defined as the time from diagnosis to clinically recorded disease progression or death from any cause. The patients were followed up according to the outpatient and electronic medical records and telephone calls. The tumor treatment strategy and the time of clinical outcome or disease progression were followed up. The disease progression was defined as the 20% increase in sum of longest diameters from nadir (and a minimum absolute increase of 5 mm), or unequivocal increase in nontarget lesions according to RECIST solid tumor standard. The progress needs to be confirmed by at least one imaging and one clinical expert. The deadline for follow-up is 2 years. The secondary endpoint was overall survival time (OS), defined as

the outcome of patient death from diagnosis to any cause or the final follow-up time. During the follow-up, the researchers conducted disease evaluation, follow up of disease progress, grip strength test, walking test, muscle density measurement and nutritional score (MNA) at 6, 12, 18 and 24 months after enrollment. If feasible, the participants will continue to be followed up for up to five years.

7、Adverse events

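### Progression assessment is not masked to sarcopenia status, although the primary PFS endpoint has a judgement component and a confirmation step that could be masked already exists

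*Combined protocol and SAP*

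**What the plan says.** The relevant text is in Section 6 (Research process), item 5 (Follow up endpoint).

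- **Endpoint.** The primary endpoint is PFS within 2 years, from diagnosis to clinically recorded progression or death. OS is secondary.
- **Definition of progression.** One route is measured: 20% growth in the sum of diameters from nadir, with at least 5 mm absolute. The other is "unequivocal increase in nontarget lesions according to RECIST solid tumor standard", which has no numerical threshold.
- **Confirmation.** "The progress needs to be confirmed by at least one imaging and one clinical expert".
- **Who does what at the visits.** At 6, 12, 18 and 24 months, "the researchers conducted disease evaluation, follow up of disease progress, grip strength test, walking test, muscle density measurement and nutritional score (MNA".

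Under Section 6, item 4, low grip strength or slow gait, together with low muscle mass, makes the sarcopenia diagnosis. Section 8 divides patients by that diagnosis and compares PFS by Kaplan-Meier and log-rank. Section 7, item 2 describes the endpoint and progression indicators as objective. Section 13 lists four roles. None is an independent or masked assessor, and one combines data collection with statistics. No section mentions masking.

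**The concern.** The people who evaluate disease also produce results that define the groups being compared, and part of the outcome rests on judgement. An assessor who knows that a patient is frail may read an equivocal non-target change as progression more readily than in a fit patient. That error would differ between groups and would run towards finding that sarcopenia worsens PFS, which is the question set in Section 2, item 3. The log-rank test takes the recorded events and dates as given, so it can neither detect nor correct such misclassification.

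This is not merely a missing detail. If the plan is followed exactly as written, the exposure remains open to bias, although a confirmation step that could be masked is already in place.

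**Working it through.** **1. The plan's own figure.** Section 5 gives 66 per group, 132 in total. Inputs: "The prevalence of sarcopenia in Asia is 25.2" (per cent), "reported correlation coefficient OR3.2 of tumor and sarcopenia", α 0.05 (two-sided assumed, since the plan does not say), power 80%, missing data up to 10%.
- Odds: 0.252/0.748 × 3.2 = 1.078, so the second proportion is 1.078/2.078 = 0.519.
- Two-proportion formula with continuity correction: 59 per group.
- Allowance for missing data: 59/0.9 = 65.6, rounded up to 66; total 132. The figure is reproduced.

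This serves only to fix the group size of 66. The odds ratio relates tumor to sarcopenia, not sarcopenia to PFS, so it says nothing about masking, and masking does not change the 132.

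**2. What is stated and what is not.**
- Stated: the same researchers evaluate disease and run the tests at the same visits; one criterion for progression is a judgement; a confirmation step exists.
- Not stated: masking of anyone; independence of the confirmers from the testers; that the confirmers run the tests; that they know the group.

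**3. Illustration of size: false calls.** The documents give no 2-year PFS and no error rate, so both are assumed. Let S be the true 2-year PFS, equal in both groups, and d the share of progression-free sarcopenic patients wrongly called as progressed, with no error in the other group. Then

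apparent HR = ln(S(1 − d)) / ln(S).

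| S | d = 5% | d = 10% |
|---|---|---|
| 0.80 | ln 0.76 / ln 0.80 = 1.23 | ln 0.72 / ln 0.80 = 1.47 |
| 0.70 | ln 0.665 / ln 0.70 = 1.14 | ln 0.63 / ln 0.70 = 1.30 |
| 0.60 | ln 0.57 / ln 0.60 = 1.10 | ln 0.54 / ln 0.60 = 1.21 |

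In patients: at S = 0.70, 66 × 0.70 = 46 sarcopenic patients are progression-free, and 5-10% of them is about 2 to 5 false calls.

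With 66 per group and a two-proportion test standing in for the log-rank test, the chance of a false positive in this direction rises from the nominal 2.5% to between 5% (S = 0.60, d = 5%) and 19% (S = 0.80, d = 10%).

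**4. What masked confirmation cannot reach.** Suppose instead that 10-30% of true events in the non-sarcopenia group are never put forward. Take a true event rate of 30% and 20% missed: the observed rate is 0.30 × 0.80 = 0.24, and the apparent HR is ln 0.70 / ln 0.76 = 1.30. Over true rates of 20-40%, the range is 1.12 to 1.56. Confirmers who see only referred cases leave this part untouched.

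**The case against.** The strongest reply is that the plan is silent on masking rather than wrong, and already has safeguards: a measured RECIST threshold, a confirmation step, and OS as secondary endpoint. Much of this stands. Target-lesion growth is measured and little exposed; deaths cannot be over-called. The exposed part is chiefly the non-target criterion, and the illustration does not subtract the rest. It also puts all the error in one group and ignores the opposite error, such as progression missed in frail patients who attend or are scanned less often.

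A reader might infer that the confirmers are the people who test grip and gait and that they know the group. The documents do not say so. The list of visit tasks belongs to the researchers collectively, and confirmation is a separate sentence. What can be said is that nothing keeps the two apart.

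A reader might also infer that masking the confirmers would remove the bias. It would not. Unmasked researchers still decide which cases go forward, and follow-up still relies on records and telephone calls. ECOG, weight, BMI and albumin, all collected under Section 6, also signal frailty, and a clinician who sees the patient is not masked by withholding a form.

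Finally, the confirmation sentence can be read as one imaging examination plus one clinical expert. On that reading no imaging reader is yet named. This affects the cost of the remedy, not the gap.

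**Conclusion.** The point holds in limited form. Progression assessment is unmasked by design, the same researchers evaluate disease and test grip, gait and MNA, and the primary endpoint has a judgement component. That leaves an avoidable bias, plausibly in the direction of the study question. Its actual size cannot be derived from the documents. The range of about 1.10 to 1.47 is a one-directional illustration that assumes no true effect, 60-80% 2-year PFS, and 5-10% false calls confined to the sarcopenia group. It is not an estimate of what will happen. The documents support neither the claim that the confirmers know the group nor the claim that masking them would eliminate the bias. The change is worth making because it is cheap and protects the primary endpoint.

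**What to change.** Add to Section 6, item 5:

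- The imaging expert and, where possible, a clinical expert who neither tests nor treats the patient confirm progression from the scans and a file without sarcopenia group, BIA, grip, gait or MNA results.
- The decision and the progression date are locked before they are linked to sarcopenia group.

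Add to Section 8, item 3 that OS will be read alongside PFS as a cross-check, since death from any cause is not open to this bias. A difference between the two would not by itself prove assessment bias, and the documents give no event rates from which to judge how precise OS will be.

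The cost is minor administration: a separate progression form and a redacted file. Patient care, sample size and endpoint definition do not change. If the confirmation sentence means an examination rather than a reader, an imaging reader must also be named.

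To reach the selection of cases as well, the masked expert could read all scheduled scans in both groups. That is an option with a real cost: up to 132 × 4 = 528 readings if a scan is done at every visit. Recording disease evaluation before that visit's physical tests would add little, because the researchers may already know the baseline diagnosis.

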Malignant tumors are often associated with weakness and cachexia. The clinical characteristic changes of tumor cachexia are continuously skeletal muscle reduction, which can not be corrected by routine dietary supplement, which may cause progressive functional decline and disorder [3]. Sarcopenia is defined as skeletal muscle mass (SMM) combined with skeletal muscle dysfunction. Now it is considered that the occurrence of primary sarcopenia is mainly related to age, and the occurrence of secondary sarcopenia is related to systemic acute and chronic diseases. In recent years, according to the latest definition of the Asian Working Group for Sarcopenia, the definition of sarcopenia has been clarified, the ICD code of the disease has been defined, and a unified diagnosis has formed [4]. Clinical studies on sarcopenia and cancer have also attracted more attention, such as digestive tract tumor, pancreatic cancer, gastric cancer, urologic tumors and rectal cancer [5][6]. Data had show that the prevalence of sarcopenia in lung cancer patients can reach as high as 43%, although sarcopenia is an elderly syndrome closely related to age, clinical rehabilitation or dietitian intervention diet can improve the nutritional status of patients with lung cancer to a certain extent. Although the diagnostic criteria of sarcopenia have been confirmed, most of the research are limited to the toxic and side effects of chemotherapy, postoperative complications and the survival rate of sarcopenia and other malignant tumors. There are few studies that have attempted to

investigate the impact of sarcopenia on the prognosis of lung cancer. Previous studies have also found that nutritional status plays an important role in tumor cachexia of other systems [7]. Loss of appetite, weight loss and fatigue caused by tumor will lead to poor nutritional status or even malnutrition. Poor nutritional status will further reduce patients' appetite and physical activity, thus forming a vicious circle. Nutrition is also an important factor in the progression of sarcopenia disease. Therefore, it is also of great clinical significance to determine whether nutritional status will affect the prognosis of patients with tumor sarcopenia, so it is absolutely valuable to investigate the risk factors associated with sarcopenia in lung cancer patients and confirm the impact of nutritional status on prognosis among these patients.

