1. During the walking test, trained doctors and nurses were trained to detect the exercise safety in the whole process. This study will practically implement the safety work and safety equipment in the implementation of the scheme, including oxygen inhalation, oximeter, defibrillator, cardiopulmonary resuscitation drugs, bronchodilators and nitroglycerin; In case of the following conditions, the test will be terminated strictly: 1. Reaching 85% of the maximum heart rate; 2. Arrhythmia events; 3. Blood pressure exceeding 180 / 100mmhg; 4. Chest pain; 5. Blurred vision; 6. Cold sweat syncope; 7. Abnormal limb coordination; 8. Blood oxygen saturation lower than 85%.
2. This study is an observational study and does not involve new drugs and traumatic testing, so there is basically no additional research risk. In case of acute exacerbation or condition change during the study, the patient may not be affected by the study and be treated in accordance with the medical principles. The end point of observation and disease progress indicators are the objective state of the development of the disease itself. The study does not involve any research methods and drugs for intervention and diagnosis measures, so there will be no serious adverse events related to the study.

8、Statistical analysis

The patients were divided into two groups according to whether they were diagnosed as sarcopenia, and the differences of clinical data between the two groups were analyzed. The statistical analysis will be calculated by spss24.0 statistical analysis software.

1. Demographic characteristics and clinical data analysis: describe the age and gender distribution of patients, group patients according to whether they are diagnosed as sarcopenia, and analyze the differences of clinical data such as age distribution, smoking, tumor type and clinical stage between the two groups. Continuous variables are represented by mean standard deviation, classified variables are represented by

percentage, students t-test analysis and Mann-Whitney U test are used according to data type differences, and chi square test is used for component comparison of classified data.

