2. Analysis of risk factors of non-small cell lung cancer combined with sarcopenia: univariate and multivariate logistic analysis of relevant variables of patients with sarcopenia, including clinical data variables, nutritional status, tumor stage, serum C-reactive protein, cholesterol level, albumin level, EGFR gene expression, etc, Logistic regression was used to analyze the risk factors of sarcopenia in non-small cell lung cancer.
3. Prognostic value of sarcopenia in non-small cell lung cancer: progression free survival time PFS and overall survival time OS were statistically analyzed by Kaplan-Meier, and the difference was tested by log-rank method.

9、 Ethics related to experiment

The risk of patients participating in this study comes from the risk of tumor itself and tumor complications. It is an observational study without any intervention means such as drugs. The study itself does not increase the disease risk of patients. Patients can still stop treatment or withdraw from the study at any time, and subjects can stop the study at any time or for any reason at their own request or at the request of the investigator. For all subjects who withdrew from the study for any reason, contact themselves or their families or health care providers 24 weeks after withdrawal to determine the subject's life status. Subjects may voluntarily stop participating in the study at any time without affecting further treatment.

At the same time, ensure that after the end of the study and midway suspension, all participants continue to accept the disease medical measures recommended in the guidelines, do not change the follow-up further treatment, and do not intervene in the outcome of the disease.

10、 Recruitment methods and informed consent of subjects

This study used the recruitment method of clinical case collection, including respiratory ward, respiratory intensive care unit and respiratory clinic. All patients must

obtain informed consent and sign the informed consent form.

11、Expected progress and completion time of the study

Study period: October 15, 2021 to October 15, 2024

From October 2021 to November 2021, the research group collected personnel training and enrolled cases.

From November 2021 to November 2023, the case observation indexes, clinical data and follow-up data were collected.

From November 2023 to January 2024, the final follow-up was completed and the outcome events were collected and sorted out.

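### Section 8 item 1 summarises every continuous variable by mean and SD and names the equal-variance t-test, although group sizes are not controlled and some markers are probably skewed

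*Combined protocol and SAP*

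**What the plan says.** Section 8 item 1 compares patients with and without sarcopenia on their clinical data. It sets one summary for continuous data: "Continuous variables are represented by mean standard deviation". Two tests follow: "students t-test analysis and Mann-Whitney U test are used according to data type differences". It names no median or quartiles, no unequal-variance test and no criterion for choosing between the two tests.

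Section 5 plans equal groups: "According to the 1:1 ratio of sarcopenia and non sarcopenia, the overall sample size is about 132", with "about 66 patients with lung cancer complicated with sarcopenia". Section 3 describes a prospective observational cohort grouped by the diagnostic criteria for sarcopenia, and section 8 repeats that grouping. No quota, matching or other means of reaching 1:1 is described.

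Two prevalence figures appear. Section 5 states "The prevalence of sarcopenia in Asia is 25.2" per cent. The background states that "the prevalence of sarcopenia in lung cancer patients can reach as high as 43" per cent.

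Section 6 item 3 collects C-reactive protein, cholesterol, albumin and four tumor markers. Section 8 item 2 lists "serum C-reactive protein, cholesterol level, albumin level, EGFR gene expression" among the candidate risk factors for the logistic model and states no measurement scale for them.

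**The concern.** Student's t pools the two sample variances. With equal group sizes, unequal SDs do almost no harm. With unequal sizes, the pooled variance is dominated by the larger group. If the smaller group is more variable, the standard error is too small and p-values are too low. If it is less variable, the reverse holds. Here the sizes depend on how many enrolled patients prove to have sarcopenia.

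The second matter is description. For a strongly right-skewed marker the mean lies well above the typical value, and the SD can exceed the mean. If such a marker is tested by Mann-Whitney, as the plan allows, the table would show a mean beside a p-value that does not test the mean.

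At stake are the comparisons of clinical characteristics under purpose 1 in section 2, not the survival analysis.

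**Working it through.** **1. The plan's own sample size.** Inputs from section 5: prevalence 25.2%, "Combined with reported correlation coefficient OR3.2 of tumor and sarcopenia", alpha 0.05 (two-sided assumed), power 80%, 10% missing.

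- Second proportion: 3.2 × 0.252 / (1 − 0.252 + 3.2 × 0.252) = 0.8064 / 1.5544 = 0.519.
- Two-proportion formula, before correction: [1.96 × √(2 × 0.3854 × 0.6146) + 0.8416 × √(0.1885 + 0.2496)]² / 0.2668² = 3.633 / 0.0712 = 51.05.
- With continuity correction: (51.05 / 4) × [1 + √(1 + 4 / (51.05 × 0.2668))]² = 58.3, so 59 per group.
- Missing data: 59 / 0.90 = 65.6, so 66 per group and 132 in total.

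The stated figure reproduces. It presupposes 66 vs 66.

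**2. Group sizes if 132 patients are enrolled and then diagnosed.**

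- At 25.2%: 0.252 × 132 = 33.3, so 33 vs 99.
- At 43%: 0.43 × 132 = 56.8, so 57 vs 75.

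**3. True error of Student's t.** Let r be the smaller group's SD divided by the larger group's SD, with the larger group's SD set to 1. The documents give no SDs, so r = 0.67 (2/3) to 1.5 is an assumption.

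- Variance that the test uses: A = {[(n1 − 1)r² + (n2 − 1)] / (n1 + n2 − 2)} × (1/n1 + 1/n2).
- Actual variance of the difference: B = r²/n1 + 1/n2.
- Large-sample two-sided error: 2 × [1 − Φ(1.96 × √(A/B))].

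For 33 vs 99 at r = 1.5:

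- A = [(32 × 2.25 + 98) / 130] × 0.0404 = 0.0528.
- B = 2.25/33 + 1/99 = 0.0783.
- √(A/B) = 0.822, so the error is 2 × [1 − Φ(1.61)] = 10.7%.

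| Split | r = 0.67 | r = 1 | r = 1.5 |
|---|---|---|---|
| 33 vs 99 | 1.7% | 5.0% | 10.7% |
| 57 vs 75 | 3.9% | 5.0% | 6.3% |
| 66 vs 66 | 5.0% | 5.0% | 5.0% |

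Simulation with normal data and equal means agrees to within a few tenths of a point. Repeat runs gave 1.7% to 1.8% and 10.2% to 10.7% at the two ends for 33 vs 99. Welch's test stayed at about 5% in every cell.

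**4. Cost of Welch when SDs are equal.** At 33 vs 99 with an assumed true difference of 0.57 SD, 100,000 simulated data sets gave power of 80.5% for Student and 79.7% for Welch. At 57 vs 75 and 66 vs 66 the two did not differ noticeably.

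**5. Mean and SD for a skewed marker.** Assume a log-normal marker with log-scale SD s. In units of the median, the mean is exp(s²/2) and the SD is exp(s²/2) × √(exp(s²) − 1).

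- s = 1: mean 1.65, SD 2.16.
- s = 1.3: mean 2.33, SD 4.89.

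In both cases mean minus SD is negative, which is impossible for a concentration.

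**The case against.** The strongest reply is that the plan already contains a rank test. A reader might infer from the mean-and-SD rule that every continuous variable will be tested with Student's t. The same sentence names Mann-Whitney, so that inference fails. Skewed markers are its natural candidates, so it does not follow that item 1 wastes their information. This stands. It leaves the summary rule untouched, and Student's t is still the test for the remaining variables.

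Second, 33 vs 99 is the least favourable case. The plan states 1:1, and 25.2% is a figure for Asia, not for this cohort. At the 43% quoted for lung cancer the distortion is small. A reader might infer that the t-test's error rate will generally double or halve. The documents do not support that: it needs both a split near 33 vs 99 and clearly unequal SDs, and no SD is given for any variable. This also stands, and it limits the size of the point. It does not restore the 1:1 split, which no procedure secures.

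Third, a reader might go on to section 8 item 2, infer that C-reactive protein enters the logistic model untransformed, and conclude that a log scale is needed to avoid losing power. Item 2 states no scale. The power gain appears when the log-odds are assumed linear in log C-reactive protein. When they are assumed linear in the raw value, the ranking reverses (at 25.2% sarcopenic, 40% power raw against 30% logged, for an assumed odds ratio of 1.6 per raw SD and log-SD 1.3). The documents support neither form, so a compulsory log transformation is not justified.

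Last, item 1 is descriptive and SPSS prints the Welch result anyway. That makes the change easy, but it does not settle which result is reported.

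**Conclusion.** The point holds in limited form. The plan prescribes mean and SD for all continuous variables and an equal-variance t-test for those not ranked, while the group sizes are left to the diagnosis. For SD ratios of 0.67 to 1.5, a nominal 5% Student's t has a true error of about 1.7% to 10.7% at 33 vs 99 and about 3.9% to 6.3% at 57 vs 75. There is no distortion at 66 vs 66 or with equal SDs.

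The error rates rest on three assumptions: the SD ratios, approximate normality, and the quoted prevalences applying to 132 enrolled patients. The description problem rests on right skew in C-reactive protein and the tumor markers, which is likely but not documented.

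The primary endpoint, progression-free survival, is analysed by Kaplan-Meier and log-rank and is unaffected. This is an inexpensive improvement to the purpose 1 comparisons, not a threat to the study's main result.

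**What to change.** In section 8 item 1:

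- Replace Student's t-test with Welch's t-test (the SPSS line for equal variances not assumed) for roughly symmetric continuous variables.
- Report median and quartiles, not mean and SD, for any variable tested by Mann-Whitney.

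Welch's test should not be applied to raw skewed markers as a substitute for Mann-Whitney. In simulated log-normal data (log-SD 1, shift of half a log-SD, 33 vs 99) its power was 37%, against 66% for Mann-Whitney.

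The cost is two short wording changes and about one percentage point of power at 33 vs 99 when SDs are equal. Section 8 item 2 need not change on this account. A log-scale analysis of C-reactive protein could be added as an optional sensitivity analysis.

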1. Identify the prevalence of sarcopenia in patients with early and mid-term non-small cell lung cancer as well as the anthropometry, clinical characteristics, tumor stage and treatment methods of this population, to compare and analyze the differences of clinical characteristics such as smoking status, tumor stage, EGFR gene expression, nutritional score and physical endurance with patients with non-small cell lung cancer.
2. Multivariate logistic analysis aim to explore the related risk factors of sarcopenia in patients with early and mid-term non-small cell lung cancer.
3. To clarify the impact of sarcopenia on the overall survival rate and progression-free survival rate of early and mid-term non-small cell lung cancer, and its clinical value as a predictor of the prognosis of patients.

3、Type of experimental design, grouping method

- 1) Study case collection scope: including respiratory ward, respiratory intensive care unit and respiratory outpatient department of Huadong Hospital Affiliated to Fudan University.
- 2) This study was a prospective, and observational cohort study. The follow-up results were grouped according to the diagnostic criteria of sarcopenia.

4、Case inclusion criteria and exclusion criteria

1. inclusion criteria

- (1) The patients with non-small cell lung cancer diagnosed by cytology or pathology meet the standards of clinical diagnosis and treatment guidelines for lung cancer of Chinese Medical Association (2018 Edition), and the TNM staging diagnosis of lung cancer meets the stage IA-IIIA.

(2) The medical records are complete.

2. exclusion criteria

- (1) Severe heart failure, acute progressive pulmonary inflammation ,acute liver and kidney dysfunction in recent 2 weeks;
- (2) Incomplete clinical and follow-up data or disagreement or inability to conduct regular follow -up CT imaging evaluation;
- (3) Patients with other malignant tumors and a history of related tumor chemotherapy within half year, previous history of radiotherapy;
- (4) Unable to stand or walk, unable to cooperate to complete the walking test, and patients with past unconscious fall history and fall risk;
- (5) Unable to complete BIA examination due to pacemaker implantation and other reasons;
- (6) Those who withdraw from the study for subjective reasons, regardless of the patient's loss of follow-up caused by any reason, shall be regarded as patients who withdraw from the study.

5、 Estimation of case sample size

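### The primary endpoint (PFS) and OS are compared only by unadjusted Kaplan-Meier and log-rank in non-randomised groups, so a difference in age or stage could be read as an effect of sarcopenia

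*Combined protocol and SAP*

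**What the plan says.** The design is an observational cohort. Section 3 says "The follow-up results were grouped according to the diagnostic criteria of sarcopenia", and section 4 admits patients for whom "the TNM staging diagnosis of lung cancer meets the stage IA-IIIA". Section 2 item 3 gives the purpose: "To clarify the impact of sarcopenia on the overall survival rate and progression-free survival rate", together with the clinical value of sarcopenia as a predictor. Section 6 item 5 makes two-year PFS primary and OS secondary.

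Section 8 has three items:

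- Item 1 is descriptive. It will "analyze the differences of clinical data such as age distribution, smoking, tumor type and clinical stage between the two groups".
- Item 2 is multivariable, but with sarcopenia as the outcome: "univariate and multivariate logistic analysis of relevant variables of patients with sarcopenia, including clinical data variables, nutritional status, tumor stage".
- Item 3 is the only analysis of either survival endpoint: "progression free survival time PFS and overall survival time OS were statistically analyzed by Kaplan-Meier, and the difference was tested by log-rank method".

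The background section states that "sarcopenia is an elderly syndrome closely related to age".

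**The concern.** A log-rank test compares the groups as they stand. In a randomised trial that is enough. Here the groups are defined by a patient characteristic that the protocol links to age and will examine for a link with stage. PFS counts death from any cause, so age can matter for the endpoint as well as stage.

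If patients with sarcopenia are older or have more advanced disease, the PFS curves can separate with no contribution from sarcopenia. Item 1 would show such an imbalance but would not remove it from the survival comparison. Item 2 does not help, because PFS and OS are not its outcomes. At stake is the main conclusion of the study: that sarcopenia affects PFS and OS, or predicts them beyond what age and stage already tell.

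**Working it through.** **The plan's own figure.** Section 5 gives 66 per group and 132 in total. Inputs: 25.2%, OR 3.2, alpha 0.05 (taken as two-sided), power 80%, 10% missing.

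- Odds: 3.2 × 0.252/0.748 = 1.078, so the second proportion is 1.078/2.078 = 0.519.
- The two-proportion formula with continuity correction gives 59 per group. Then 59/0.9 = 65.6, so 66 per group and 132 in total.

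The figure reproduces. It compares two proportions using an odds ratio between tumour and sarcopenia. It sets no PFS hazard ratio or event count and makes no allowance for covariates. The 1:1 ratio is a ratio of group sizes; no matching variable is named.

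**Stage as confounder (assumed inputs).** The documents give no stage mix, event rates or imbalance. Assume stage I/II/IIIA shares of 55/20/25%, two-year PFS event risks of 10/30/50%, and no sarcopenia effect within stage.

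Overall risk = 0.55×0.10 + 0.20×0.30 + 0.25×0.50 = 0.24, so 132 × 0.24 = 31.7 events.

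Worked case, sarcopenia prevalence 15/30/50% by stage:

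- Share with sarcopenia: 0.0825 + 0.06 + 0.125 = 0.2675.
- Risk with sarcopenia: (0.0825×0.10 + 0.06×0.30 + 0.125×0.50)/0.2675 = 33.2%.
- Risk without: (0.4675×0.10 + 0.14×0.30 + 0.125×0.50)/0.7325 = 20.6%.
- Approximate crude HR = ln(1 − 0.332)/ln(1 − 0.206) ≈ 1.7.
- Events at 66:66: 66 × (0.332 + 0.206) ≈ 35.5.

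The other rows follow in the same way. Rejection rates come from simulation: exponential times, censoring at two years, N = 132, nominal 5% test. Ranges cover repeated runs at 66:66 and at natural prevalence.

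| Prevalence by stage I/II/IIIA | Risk with / without sarcopenia | Crude HR | Events at 66:66 | Unadjusted log-rank rejects | Stage-stratified rejects |
|---|---|---|---|---|---|
| equal | 24.0% / 24.0% | 1.0 | 31.7 | 4–5% | about 5% |
| 20/25/35% | 28.2% / 22.6% | 1.3 | 33.5 | 10–12% | about 5% |
| 20/30/45% | 30.2% / 21.6% | 1.5 | 34.2 | 19–22% | about 5% |
| 15/30/50% | 33.2% / 20.6% | 1.7–1.8 | 35.5 | 34–38% | about 5% |

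The stratified rates varied between about 4% and 7% from run to run.

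**A simpler confounder.** Assume one binary risk factor, present in 40–60% of the sarcopenia group and 20% of the other, with HR 2–4 and a two-year risk of 10–20% in low-risk patients. The crude HR is 1.16–1.77 and the unadjusted test rejects in 6–49% of runs; the stratified test rejects in about 4–6%.

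**Age alone.** Assume SD 9 years, a sarcopenia group 5 to 8 years older, HR 1.2 to 1.5 per 10 years, 66:66, baseline two-year risk 24%. The crude HR is 1.09 to 1.36 and rejection 6% to 15%. After adjustment for age the HR is about 1.0 and rejection 4–5%.

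**The proposed model.** A Cox model with sarcopenia, stage (two terms) and age was simulated with stage and a 5-year age gap (HR 1.3 per 10 years) acting together. It rejected in 5–6% of runs. Adjustment widened the standard error of the sarcopenia log HR by about 5% to 11%.

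**The case against.** Section 8 item 3 is headed as prognostic value, and the background speaks of observing a correlation with prognosis. For a crude prognostic association, Kaplan-Meier with log-rank is a valid description. That stands, and the fix keeps it. It does not meet section 2 item 3, which aims at the impact of sarcopenia and its value as a predictor; the expected goals in section 13 repeat this.

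The largest inflation figures come from stage, which item 2 lists only as a candidate factor, with no direction or size. The confounder best supported by the text is age, and there the inflation runs from almost nothing to moderate. This also stands: no single simulated figure should be quoted as the expected bias. The gap in the plan does not depend on any of them.

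Events may be fewer than the count for 132 patients. If the 10% allowance is used up and 118 are evaluable, the same rates give about 28 to 32 events. Power is low in any case. For an assumed true HR of 2 at 1:1 with 28.5 to 35.5 events, Φ(ln 2 × √(D/4) − 1.96) gives 46–54% unadjusted, and 38–50% once the standard error is widened by 11% to 5%. Adjustment costs some power, but the unadjusted test is also well short of 80%.

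**Conclusion.** The concern holds. The only planned analysis of PFS and OS is unadjusted, the groups are not randomised, and nothing in the plan could separate sarcopenia from age or stage. This follows from the text alone.

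The size is illustrative. With no true effect, the false-positive rate of the log-rank test is about 10–38% under the assumed stage imbalances and 6–15% under the assumed age differences; it stays near 5% if the groups happen to be balanced. Because the gap concerns the primary endpoint and the central claim, it should be corrected before the analysis.

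**What to change.** - **Primary analysis.** Prespecify a Cox model for PFS with sarcopenia, stage (I, II, IIIA) and age, reporting the adjusted HR with 95% CI.
- **Unadjusted results.** Keep Kaplan-Meier curves and the log-rank test as description. Add a stage-stratified log-rank as a simple supporting test.
- **OS.** Use the same model if events allow, with the minimum event count for doing so written down in advance.
- **Sensitivity analyses.** Add ECOG and smoking one at a time.
- **Treatment strategy.** Leave it out of the primary model and say why: it is chosen after diagnosis and may itself depend on sarcopenia. This is a judgement and should be presented as one.
- **Nutritional status (secondary).** The background also aims at nutritional status and survival, which has no survival analysis and is not among the numbered purposes. If it is kept, add baseline MNA in a secondary Cox model.

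**Cost.** Protocol wording and a few lines of analysis. Section 6 already records age, "tumor stage at the time of diagnosis", ECOG, smoking and MNA. The constraint is events: four coefficients share about 32 to 36 events (8 to 9 each) under the assumed rates, or 28 to 32 (7 to 8 each) with 118 evaluable patients, and there will be fewer for OS. A longer covariate list is not supportable, and the report should state the limited power.
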